3. STUDY DESIGN

We will use a stepped-wedge randomised controlled trial (RCT) design (Hemming, Haines, Chilton, Girling, & Lilford, 2015). This design involves random and sequential crossover of groups from control to intervention until all groups are exposed to the intervention. A stepped wedge cluster RCT is especially useful when the intervention is thought to do more good than harm (i.e., when there is no equipoise). In that situation, it is unethical to withhold or withdraw the intervention from a proportion of the subjects as would occur in a parallel group or classic cluster RCT. Besides, it may be impossible to implement the intervention in half of all clusters simultaneously because of practical, logistical, or financial reasons, which is also the case in the current study with regard to the practical and logistical reasons. Then, the stepwise treatment implementation of the stepped wedge design offers a solution. Since all patients included in this study will be offered the intervention, which may contribute to limiting lost to follow-up

The personalized approach, local collaborations with the social domain and organizational differences between general practices will result in nuanced differences in how our intervention will be applied. Besides, training the Positive Health methodology and the enhanced collaboration between domains most likely effects patients not-offered the intervention as well. Randomisation will therefore be done by cluster.

This study will be performed in 20 general practices. Each practice will form one cluster. We aim to include an average of 10 patients per cluster. A GP or POH-GGZ can only participate in one cluster. The terms GP practice and cluster will be used alternatively and exchangeable from this point on, both referring to the given description.

Each participating patient starts with a control period and will cross-over to the intervention period. The control period varies between 2 to 8 months. All patients from a GP practice cross-over at the same moment. Therefore the GP-practices are randomized into one of four groups.

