5. METHODS

5.1 Study parameters/endpoints

5.1.1 Main study parameter/endpoint

The main study parameter is incremental cost-effectiveness. To measure this outcome several data sources will be used and linked at the individual level.

Costs and utilisation of care during the trial

At the start of the study (t=0) and at the end (t=22) data on care usage and costs will be collected. Data on medical and acute care utilization for individual patients will be obtained from HIS and CBS microdata, supplemented with patient reported data. A selection of relevant (potential) costs for this population is made via expert opinion. The patient reported data consist only of data not available in HIS, for which questions were selected from the iPCQ, iMCQ and TiC-P questionnaires (See F1). Items with limited effect on cost of care which were not retrievable from HIS or microdata were excluded (See F1).

These data will be translated into cost using standard cost prices from the Dutch guideline for economic evaluations. The datasets containing coded data will be stored on the I-Drive of the LUMC for a period of 15 years. This drive is secured and only accessible by the researchers. Baseline characteristics from patients as well as information collected from the questionnaires will also be securely stored in an online database, named CASTOR.

Cost and utilisation of care previous to trial

The medical data from 3 years prior to the start of the study will be used to analyse the costs and utilisation of care. This extended period used for data analysis was deliberately chosen to include a timeframe during and before the SARS-CoV-2 pandemic. It is yet unknown how the pandemic and its subsequent measures affected our population and their usage of care.

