Data on cost of care and care utilization prior to the start of the trial is retrieved from CBS microdata (Statistics Netherlands). Data from several sources are linked at a personal level by Statistics Netherlands in a secured remoted access environment. Data in the CBS microdata environment is secured by using a linkage key. All data in this environment is pseudonymized and data extraction is checked by Statistics Netherlands on traceability. By doing this, the privacy and linkage on individual level is secured. The proposed linkages in this proposal are in accordance with the General Data Protection Regulation (GDPR), as Statistics Netherlands is allowed by law to link data sets under strict disclosure condition (The European Parliament & the Council of the European Union, 2016).

Quality of life

The EQ-5D-L5 will be used to provide the quality of life measures in this study. This questionnaire is used to define health in terms of 5 dimensions: self-care, usual activities, mobility, anxiety/depression and pain/discomfort. It is also possible to define unique health states with this questionnaire, as each domain has five answer levels ranging from no problems to extreme problems (Versteegh et al., 2016). Besides being short and easy to comprehend, the questionnaire is also validated. In addition, quality of life will also be assessed by using the validated SF-12 (12-items), including 8 dimensions, namely: bodily

pain, vitality (energy and fatigue), general mental health (psychological distress and well-being), general health perceptions, limitations in physical activities because of health problems, limitations in social activities because of physical or emotional problems, limitations in usual role activities because of emotional problems, and limitations in usual role activities because of physical health problems (Turner-Bowker et al., 2014).

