6. STATISTICAL ANALYSIS

Before analysis, all data will be cleaned improving data quality.

Quantitative data:

We will conduct intention-to-treat and per protocol analysis. We will use multilevel generalized linear models with the patient as the first level to correct for the repeated measures. The GP-practice (or cluster) will be the second level, and the group in which the GP practice is randomized will be the third level. We will adjust for level of integration, neighbourhood, time from start of study (continuous; with an interaction between cluster and time so that each cluster had its own underlying time trend), and total time on the randomised intervention, with time before intervention given as zero (continuous). Based on ICPC-codes used to select eligible patients, we will explore if subgroups can be identified in mainly (chronic) somatic, mainly mental or mainly social problems. Furthermore, analyses/ results will be stratification for sex. The analysis of the implementation will be descriptive.

Cost-effectiveness analysis/budget impact analysis:

The economic evaluation will consist of a trial-based cost-utility analysis (cost per QALY) with a time horizon of one year and a cost-utility analysis with a lifetime horizon (cost per QALY). Both analyses will be performed from a societal perspective. Next to this a Budget Impact Analysis will be performed according to the ISPOR Task Force principles.

Qualitative data:

Qualitative data will be collected through interviews or focus groups with care providers and patients and audiorecording. The interviews and focus groups will be conducted using a topic list based on experience of the pilot (protocol number **NL8223-10216**) and literature, to determine their satisfaction with the new approach.

The collected qualitative data will be analysed using both an inductive and deductive approach. This will be done by first transcribing the data and doing a thematic content analysis. After this, the data will be put into an initial coding book and further analysed until a final coding book is formed. The deductive analysis will be done using the positive health methodology. We will analyze whether positive health topics and techniques are being discussed and applied, as recommended by the methodology.

The audiotapes will be scored by two independent observers using the validated OPTION5 questionnaire.

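### Three years of individually linked pre-trial costs are planned but have no defined role in the effect analysis and are absent from the stated adjustment list; adding them as covariates is a small, cheap improvement.

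*Protocol*

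**What the plan says.** Protocol section 5.1.1 states: "The medical data from 3 years prior to the start of the study will be used to analyse the costs and utilisation of care". The Objectives chapter repeats this. The only reason given for the three-year span is to cover time before and during the pandemic. On the source, section 5.1.1 says: "Data on cost of care and care utilization prior to the start of the trial is retrieved from CBS microdata", with linkage at the level of the person.

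Section 6 specifies "multilevel generalized linear models with the patient as the first level to correct for the repeated measures", with practice and randomised group as higher levels. It names its covariates, beginning: "We will adjust for level of integration, neighbourhood, time from start of study". Calendar time is further specified "with an interaction between cluster and time so that each cluster had its own underlying time trend". The one remaining item is a continuous exposure-time term, set to zero until the switch. Prior cost is not among them. The paragraph on the cost-utility analysis, with its one-year horizon, names no covariates.

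Section 3 says "Each participating patient starts with a control period and will cross-over to the intervention period", with control periods of 2 to 8 months and five practices in each of four groups. Section 4.4 assumes 20% loss to follow-up. Section 5.6 stops data collection when a patient withdraws.

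**The concern.** Costs in this population vary widely: section 4.4 gives an SD of €24,585 on a mean of €22,494. With five practices per group, sizeable chance differences in cost between groups are likely. A patient's own earlier cost is fixed before any switch to the intervention, so it is a legitimate baseline covariate, and its retrieval is already planned. Leaving it out forgoes a little precision, some protection against imbalance in the between-practice part of the estimate, and information on patients who leave early.

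There is a second issue. Because the three years have no defined role, the wording of section 5.1.1 would also permit their use as a before-period comparator. Section 4.2 selects patients on at least two acute care encounters in the past 12 months. The introduction itself names regression to the mean as a weakness of the pilot, so a before-after reading of these costs would be exposed to the same bias.

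**Working it through.** **1. The plan's own figure.** The design effect in section 4.4 (one baseline measure, 4 steps, 10 patients per cluster, ICC 0.1) is

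[1 + 0.1(40 + 10 − 1)] / [1 + 0.1(20 + 10 − 1)] × 3(1 − 0.1) / [2(4 − 1/4)] = (5.9/3.9) × (2.7/7.5) = 0.545.

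The protocol states 0.54. The layout is therefore read correctly, and the sample size takes no credit for covariate adjustment.

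**2. Size of chance imbalance.** With five practices of 10 patients per group, ICC 0.1 and the stated SD, the chance SD of the difference in mean annual cost between two groups is

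€24,585 × √[2 × (0.1/5 + 0.9/50)] = €24,585 × √0.076 ≈ €6,800.

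The target effect is 0.25 × €22,494 ≈ €5,600. This is not the standard error of the trial's effect, because within-patient crossover removes much of it. It shows what the between-practice part is exposed to.

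**3. Precision gain in the planned type of model.**

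*From the protocol:* 20 practices, 10 patients each, four switch times (t = 2, 4, 6, 8), ICC 0.1.

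*Assumed, since the protocol gives no figures:*
- Total variance is 1, with practice variance 0.1, patient variance s − 0.1 and residual variance 1 − s.
- The within-person correlation s runs from 0.2 to 0.7.
- Prior cost explains a share e of the stable variance, from 30% to 70%. Adjustment multiplies the explained components by 1 − e.
- The randomised-group level is left out.

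The variance of the effect is the matching diagonal element of (Σ X′V⁻¹X)⁻¹, summed over practices. The table gives adjusted variance divided by unadjusted variance for five two-monthly periods.

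| Mean model | Patient variance explained only | Patient and practice variance explained |
|---|---|---|
| Categorical time, on/off effect | 0.990-0.998 | 0.89-0.99 |
| Practice-specific trends, on/off effect | 0.991-0.998 | 0.93-0.99 |
| Practice-specific trends, exposure time | 0.996-0.999 | 0.97-1.00 |

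The last row is closest to section 6. With eight assumed measurement times up to t = 22, its ratios are 0.999-1.000 and 0.99-1.00.

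**4. Edge of the range.** Take s = 0.3 and a correlation of 0.5 between prior and trial cost, so that e = 0.25/0.3 = 83% at both levels. The five-period ratios are then 0.84, 0.90 and 0.95 for the three models. Random monotone dropout of 20% moves the ratios by about 0.02 at most.

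**The case against.** The strongest counter-case is that section 6 contains no wrong statement. A list of adjustment variables does not forbid others, and a separate analysis plan, not shown here, could add prior cost. That stands in so far as this is an improvement and not a contradiction. But section 6 does name a list, and the three years have no stated role in the effect analysis. The suggestion therefore changes something written and does not ask for routine detail.

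The second objection is that the gain is near zero. That largely stands for precision, as the working shows. On imbalance, every practice contributes to both conditions, so only the between-practice part of the estimate is affected. On loss, a likelihood-based multilevel model already conditions on earlier observed outcomes, so prior cost adds to existing protection. For a patient in the first group who leaves early, however, the control information may cover only about two months.

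Three stronger readings are tempting, and the protocol does not support them:

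- A reader might expect the variance to fall by the squared correlation, as with one outcome per patient, or by the amount found when groups are compared within one period. Section 6 plans neither analysis, and every patient crosses over. From month 8 all groups are on the intervention, so there is no concurrent one-year comparison of groups either.
- A reader might think the patient effect is informed only by the short control period. It draws on all 7 or 8 measurements, which is why a time-constant covariate adds so little.
- A reader might take prior cost to be the best predictor of trial cost, available for everyone. The protocol gives no correlation and does not state that linkage is complete. Selection on recent use and the pandemic years may weaken the association.

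**Conclusion.** The point holds as a minor improvement. Pre-trial costs linked to individuals are planned, are missing from the adjustment list in section 6, and have no defined role in estimating the effect.

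The expected fall in variance is about 0-1% if prior cost explains only patient-level variance and roughly 1-11% if it explains practice-level variance too. It is about 0-3% with the trends and exposure-time term that section 6 specifies, or 5% at the most favourable setting tried. These ranges rest on assumed within-person correlations and explained shares, and on variance components treated as known.

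The case for the change rests mainly on two other benefits, neither quantified for the planned model. One is some further protection against chance imbalance among five practices per group. The other is a more credible missing-at-random assumption when data collection stops at withdrawal. A stated role also closes off a before-after use of the data. The omission does not make the planned analysis invalid.

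**What to change.** Add a sentence to section 6, or to the analysis plan, that enters each patient's pre-trial annual costs as prespecified fixed covariates in the cost model and in the one-year cost-utility analysis. Enter them by year, for example log-transformed. Separate years let the selection-inflated last year carry its own coefficient. Define the years so that they end before t = 0, and say how patients who cannot be linked are handled.

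Add a second sentence stating that these years serve as covariates only and not as a usual-care comparator, because patients are selected on at least two acute care encounters in the past 12 months and regression to the mean is expected.

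The cost is about three degrees of freedom and no new data collection, since retrieval and linkage are already planned. The sample size need not change, and no credit for the adjustment should be taken in it.

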5.1.2 Secondary study parameters: Patient experience of care

The secondary study parameter is insight into the patient experience of care. To assess their experience focus groups will be organized. A questionnaire on experience of care has been considered, but no appropriate and validated questionnaires for this population are available. Therefore, the format of a focus group was chosen. Focus groups will be organized at 4 different timepoints (t=14, t=16, t=18 and t=20) and each focus group will consist of 6 to 12 patients. For each timepoint several focus groups will be organized. The exact size of the group and number of organized groups, will depend on the number of patients that choose to participate. Four main topics will be discussed, namely: care before the new approach, the new approach, the collaboration between the professionals and the experienced effects of the new approach (see F1).

The presence of proactive coping skills will be quantitatively measured with the *Utrechtse Proactieve Coping Competentie lijst* (UPCC). This is a 21-item questionnaire that measures self-rated proactive coping competences. The questionnaire has been validated in different adult Dutch patient groups. (Bode et al., 2008) (see F1).

Self-efficacy will be measured using two different instruments. The first is the validated Patient activation Measure (PAM-13). This is a 13-item instrument that measures self-reported knowledge, skills and confidence in managing one's health. With this instrument patients can be categorized in four levels of activation (Hibbard et al., 2005). The second questionnaire is the Self-efficacy and Intention itemlist (SE+IN Itemlist). This measures (action and maintenance) self-management self-efficacy, the intention to perform certain self-management behaviors and the presence of certain self-management behaviors. This itemlist was specifically created for this study, as there aren't any questionnaires that are geared towards understanding behavior change in this complex and heterogeneous group of patients. The itemlist consists of 22-items and was created using the Health Action Process

Approach (HAPA) model (to determine the constructs that need to be measured) (Schwarzer, 2016), a combination of literature and conversations with care professionals (to determine relevant self-management behaviors that these patients seem to lack) and other questionnaires with elements of self-management self-efficacy (Ludman et al., 2013; Bodenheimer, Lorig, Holman, & Grumbach, 2002; Lorig, Halsted, & Holman, 2003).

5.1.3 Secondary study parameter: Process evaluation

A process evaluation of this study will be done simultaneously, as a process evaluation can provide valuable insight on the practicalities of the intervention. This information is useful for future implementation of this intervention. Data on recruitment and reach of the population will be gathered during the inclusion of patients in this study, and on shared decision making will be gathered during the intake and MDO.

All involved care professionals in this study will be invited to participate in a focusgroup (see E1 and F1). These focusgroups will be held at four different timepoints (t=14, t=16, t=18 and t=20). Through focusgroups with the involved care professionals the following themes of process evaluation will be discussed:

- Fidelity (the extent to which the intervention is executed conform protocol)
- Dose delivered (the extent in which the intervention is offered)
- Dose received (the extent in which the patient received the offered care)
- Context (other factors not related to this protocol that might have an influence on the outcomes)
- Satisfaction (the extent to which the care providers are satisfied with the intervention and procedures)

During this study information of each GP practice will be gathered on the level of integration of care with the social and mental domain. This will be done using an adapted *integratiemeter* (Broesveld et al., 2016). The level of integration with the social, mental and somatic domain will be determinant based on an (minor) adapted version of the *integratiemeter* from Broesveld et al. (2016). The wording of this questionnaire has been very slightly altered to fit our population (see F1).

Additionally, information about acceptability, feasibility, appropriateness, and perceived and experienced effectiveness of the intervention will be gathered from care professionals from participating as well as non-participating practices. This will be done before the intervention starts and right after the intervention for each group of GP's. Acceptability, appropriateness, and feasibility will be measured using the The Acceptability of Intervention Measure (AIM), Intervention Appropriateness Measure (IAM), and Feasibility of Intervention Measure (FIM) four-item measures of implementation outcomes that are often considered "leading indicators" of implementation success (Weiner et al., 2017; Proctor et al., 2011). The FIM, AIM, and IAM have been translated and backtranslated for this study. Perceived and experienced effectiveness of the intervention will be measured with one item (see F1).

To assess the patients' experiences with the intervention and their care coordinator an adjusted version of the Net Promoter Score (2 item questionnaire) will be administered (Reichheld, 2003). Furthermore, the patients' perceptions of the degree to which their

healthcare provider is autonomy supportive will be assessed using the 6 item Health Care Climate Questionnaire (Jochems et al., 2014; Czaikowska et al., 2017) (see F1). Level of shared decision making will be based on audio recorded which will be scored by two independent observers using the validated OPTION5 questionnaire. If a participant is not comfortable with these recordings, the recordings may be skipped without further consequence for study participation.

5.2 Randomisation, blinding and treatment allocation

Randomisation happens twice in this study. First, clusters are randomised evenly into one of four groups (see chapter 3), which corresponds with duration of control period. Every 2 months a new group will start with the intervention, until all groups have received the intervention. The first group will start 2 months after the start of the study. A specifically designed randomisation tool using *Microsoft Excel* is used. We randomise clusters *en bloc*.

The second randomisation is to determine the order in which selected patients are approached. While identifying eligible patients, we end with a selection of patients who fall under 1 of 3 categories: (1) eligible per GP-list and per algorithm, (2) eligible per GP list and (3) eligible per algorithm. We aim to equally include patients from the GP's selection and the algorithm's. The internal order of these lists are randomized using a specifically designed randomisation tool using *Microsoft Excel*. First, those who appear on the list of both GP and algorithm are approached for study participation. Then, recruitment alternates between the GP-list and the algorithm list to acquire a 50/50 divide.

